6 STUDY PROCEDURES

6.1 Patient Eligibility, Pre-Screening and Exclusions

All patients presenting to the Investigators with Budapest criteria, research subset¹, for the diagnosis of Complex Regional Pain Syndrome at an infraumbilical location who have not had an adequate response to a course of conservative management including analgesics and physical therapy will be screened for eligibility. A Screening/Enrollment Log will be utilized in order to maintain a cumulative tracking of all screened patients.

Patients must meet all inclusion/exclusion criteria for enrollment in the clinical study. Reasons for screening failure(s) will be documented.

6.1.1 Inclusion Criteria

Patients must meet ALL of the following criteria to be eligible for participation in the study:

- Patient is greater than 18 years of age
- An infraumbilical location of the index pain
- Symptoms have been present for greater than 6 months
- Continuing pain which is disproportionate to any inciting event
- Report hyperesthesia and/or allodynia
- Report vasomotor changes including temperature asymmetry and/or skin color changes and/or skin color asymmetry
- Report edema and/or sweating changes and/or sweating asymmetry
- Report decreased range of motion and/or motor dysfunction (weakness, tremor, dystonia) and/or trophic changes (hair, nail, skin)

¹ To make the clinical diagnosis of CRPS using the “research subset” patients must have at least one symptom in all four symptom categories and at least one sign (observed at evaluation) in two or more sign categories.

1. Continuing pain, which is disproportionate to any inciting event

2. Must report at least one symptom in three of the four following categories:

- Sensory: Reports of hyperesthesia and/or allodynia
- Vasomotor: Reports of temperature asymmetry and/or skin color changes and/or skin color asymmetry
- Sudomotor/Edema: Reports of edema and/or sweating changes and/or sweating asymmetry
- Motor/Trophic: Reports of decreased range of motion and/or motor dysfunction (weakness, tremor, dystonia) and/or trophic changes (hair, nail, skin)

3. Must display at least one sign at time of evaluation in two or more of the following categories:

- Sensory: Evidence of hyperalgesia (to pinprick) and/or allodynia (to light touch and/or temperature sensation and/or deep somatic pressure and/or joint movement)
- Vasomotor: Evidence of temperature asymmetry (>1°C) and/or skin color changes and/or asymmetry
- Sudomotor/Edema: Evidence of edema and/or sweating changes and/or sweating asymmetry
- Motor/Trophic: Evidence of decreased range of motion and/or motor dysfunction (weakness, tremor, dystonia) and/or trophic changes (hair, nail, skin)

4. There is no other diagnosis that better explains the signs and symptoms (Harden, et al. 2007)

- Display at least one sign in two or more of the following categories:
 - Sensory: Evidence of hyperalgesia (to pinprick) and/or allodynia (to light touch and/or temperature sensation and/or deep somatic pressure and/or joint movement)
 - Vasomotor: Evidence of temperature asymmetry ($>1^{\circ}\text{C}$) and/or skin color changes and/or asymmetry
 - Sudomotor/Edema: Evidence of edema and/or sweating changes and/or sweating asymmetry
 - Motor/Trophic: Evidence of decreased range of motion and/or motor dysfunction (weakness, tremor, dystonia) and/or trophic changes (hair, nail, skin)
- Patient failed to have resolution of symptoms despite at least 4 weeks of conservative management including analgesic pharmacotherapy and physical therapy
- Patient has index site pain \geq spine pain
- The subject is physically and mentally able and willing to participate in the study
- Patient is willing and able to provide informed consent

6.1.2 Exclusion Criteria

All patients who meet any of the following Exclusion Criteria should not be enrolled into the study:

- Previous surgery to the spine which could compromise placement of the study device
- Anatomical abnormality including severe central canal stenosis or bony foraminal impingement which could preclude device placement
- Foreseen need for MRI to monitor or evaluate another chronic condition
- Previous experience with neuromodulation (spinal cord stimulation, peripheral nerve stimulation) for the treatment of pain at the index location
- Active local or systemic infection
- Actively in litigation for pain symptoms
- Currently on Workman's Compensation for a pain complaint at the index site
- Women who are pregnant or intend to become pregnant during the study duration

6.2 Enrollment and Written Informed Consent

Patients who pass the initial pre-screening will be asked to sign the study-specific IRB - approved Informed Consent form before any study-specific tests or procedures are performed. The investigator will inform the potential subject of the elements of the clinical

study including, risks, potential benefits and required follow-up procedures prior to obtaining the potential subject's informed consent.

6.3 Randomization

After informed consent has been obtained, patients will be randomized in a 1:1 ratio to one of two treatment groups: Dorsal Column Stimulation or Dorsal Root Ganglion Spinal Cord Stimulation. The investigator will be given numbered, sealed envelopes with a slip inside that discloses the patient assignment.

If a patient randomized to either group refuses the proposed treatment plan, they will be removed as a study participant. Patients withdrawing from the study due to randomization assignment will receive standard care with a new randomization code being assigned to the next enrolled study patient.

Investigators, their study staff, as well as study subjects will not be masked to the assigned study device. Observers will record sensory deficits to touch, pain, temperature, motor strength of major muscle groups, patient reflexes (0-4 scale), analgesics doses and frequency, and radiographic assessments if necessary. Subjects will complete the patient questionnaires at each follow-up visit.

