	
 • Safety defined as adverse events related to the procedure or devices
Inclusion Criteria	
All patients must meet all of the following Inclusion Criteria to be eligible to be enrolled into the study:
 
 • Patient is greater than 18 years of age • An infraumbilical location of the index pain • Symptoms have been present for greater than 6 months • Continuing pain which is disproportionate to any inciting event • Report hyperesthesia and/or allodynia • Report vasomotor changes including temperature asymmetry and/or skin color changes and/or skin color asymmetry • Report edema and/or sweating changes and/or sweating asymmetry • Report decreased range of motion and/or motor dysfunction (weakness, tremor, dystonia) and/or trophic changes (hair, nail, skin) • Display at least one sign in two or more of the following categories: 
 ○ Sensory: Evidence of hyperalgesia (to pinprick) and/or allodynia (to light touch and/or temperature sensation and/or deep somatic pressure and/or joint movement) ○ Vasomotor: Evidence of temperature asymmetry (>1°C) and/or skin color changes and/or asymmetry ○ Sudomotor/Edema: Evidence of edema and/or sweating changes and/or sweating asymmetry ○ Motor/Trophic: Evidence of decreased range of motion and/or motor dysfunction (weakness, tremor, dystonia) and/or trophic changes (hair, nail, skin) • Patient failed to have resolution of symptoms despite at least 4 weeks of conservative management including analgesic pharmacotherapy and physical therapy • Patient has index site pain \geq spine pain • The subject is physically and mentally able to participate in the study • Patient is willing and able to provide informed consent • Patient is willing and able to comply with the study protocol
Exclusion Criteria	
All patients who meet any of the following Exclusion Criteria should not be enrolled into the study:
 
 • Previous surgery to the spine which could compromise placement of the study device

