4 STUDY ENDPOINTS

The following endpoints will be evaluated in all patients enrolled in the study.

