5.2 Sample Size and Number of Centers

The study will be conducted a single center with a target maximum of 62 patients (31 randomized to each group).

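### Section 6.3 removes and replaces randomised patients who refuse their device in an unmasked trial, and no all-randomised set is defined, so the noninferiority result can depend on who refuses which arm

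*Combined protocol and SAP*

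**What the plan says.** - **Removal (6.3):** "If a patient randomized to either group refuses the proposed treatment plan, they will be removed as a study participant". Those who leave because of their assignment get standard care, "with a new randomization code being assigned to the next enrolled study patient".
- **Masking (6.3):** "Investigators, their study staff, as well as study subjects will not be masked to the assigned study device". The slip in the sealed envelope discloses the arm.
- **Who is evaluated (4):** "The following endpoints will be evaluated in all patients enrolled in the study". Section 6.2, headed "Enrollment and Written Informed Consent", places enrolment at consent, and 6.3 randomises after consent. A refuser is therefore already enrolled when removed.
- **Analysis (8.1 to 8.4):** a Blackwelder noninferiority test of responder rates at one-sided 0.05 with a 5-point margin. No all-randomised or per-protocol set is defined, and there is no rule for counting refusers.
- **Numbers:** section 5.2 caps the trial at 62, 31 per arm, without saying whether a refuser counts. The heading of 6.7 mentions replacement, but its text gives no rule for it.
- **Safeguards:** 6.1.1 requires that "The subject is physically and mentally able and willing to participate in the study", and the synopsis inclusion criteria add "Patient is willing and able to comply with the study protocol". Section 11.3 checks understanding before consent. Section 6.7 expects few withdrawals and records the reasons.

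**The concern.** This is exclusion after randomisation for a reason that depends on the arm. Patients and staff know the device when the refusal is made, so refusers in one arm need not resemble refusers in the other. Once they are gone and replaced, the two groups are no longer simply the groups that randomisation formed.

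Sections 4 and 6.3 also pull apart: one evaluates everyone enrolled, the other removes some of them from the study. Section 8 does not settle which prevails. A removed patient has no planned follow-up, so the gap could not be repaired at analysis.

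With a 5-point margin and about 26 analysed per arm, one patient is nearly 4 points (1/26 = 3.8%). Even a few one-sided refusals could therefore affect the primary claim.

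**Working it through.** **Inputs from the plan.** DRG 81%, SCS 56%, 15% attrition, power above 70% (8.3); one-sided 0.05, so critical z = 1.645, and margin 0.05 (8.4); 31 per arm (5.2). 31 × 0.85 = 26.35, so about 26 analysed per arm. **Assumed:** the number of refusals k and how refusers would have responded.

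**The plan's own power.** With unpooled variance, power = Φ[(p_D − p_S + 0.05)/SE − 1.645].
- n = 26: SE = √(0.81×0.19/26 + 0.56×0.44/26) = 0.1241; 0.30/0.1241 = 2.418; power 78.0%.
- n = 31: 84.0%.

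Both agree with the figure in 8.3.

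**Shift in one arm's rate.** Completers respond at rate p, the k refusers would all fail, and they are removed and replaced. Shift = p·k/(n + k).
- DRG, k = 2: 0.81×2/33 = 4.9 points (31 analysed); 0.81×2/28 = 5.8 (26 analysed).
- SCS, k = 3: 0.56×3/34 = 4.9; 0.56×3/29 = 5.8. This has the opposite effect on the noninferiority claim.
- One to three failing refusers in each arm: the difference moves by 0.25·k/(n + k), or 0.8 to 2.6 points.

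**Type I error, two DRG refusers removed, n = 26.** The true all-randomised DRG rate is set 5 points below SCS: 0.51 when SCS is 0.56. The completers' rate c follows from what the refusers would have done.

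| Refusers would respond | c | Type I error |
|---|---|---|
| Not at all | 0.51×28/26 = 0.549 | Φ(0.0392/0.1378 − 1.645) = 8.7% |
| At half the completers' rate | 0.51×28/27 = 0.529 | 6.6% |
| At the SCS rate | (0.51×28 − 2×0.56)/26 = 0.506 | 4.7% |

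If neither would respond, other SCS rates give 7.4% at 40% and 8.1% at 50% (the range section 1.1 gives for dorsal column stimulation in CRPS), and 13.5% at 81%.

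**SCS refusers removed.** Here 56% is taken as the all-randomised SCS rate. Two failing refusers removed lift the completers' rate to 0.56×28/26 = 0.603. Power = Φ(0.2569/0.1230 − 1.645) = 67%, down from 78%.

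**A result near the planned rates.** 21/26 v 15/26 gives z = 2.27. Restoring failing DRG refusers gives 2.00 (21/27), 1.76 (21/28) and 1.55 (21/29). The third reverses the conclusion; if one of the three responds (22/29), z = 1.85 and it stands.

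**Counting missing SCS refusers as failures.** Suppose two SCS refusers would respond at 56% but are scored as failures. SCS is then analysed at 0.56×26/28 = 0.52 on 28 patients. With true DRG 0.51 on 26, type I error = Φ(0.04/0.1361 − 1.645) = 8.8%.

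**The case against.** The case for leaving the rule alone has real content.

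- **Refusals may be rare.** The willingness criteria, the consent process and the expectation in 6.7 all point that way, and two refusals would be 6.5% of an arm of 31. This stands as a reason to treat the harm as conditional. It does not remove the harm: no safeguard asks whether the patient would accept either device, and 6.3 makes specific provision for refusals.
- **Refusers may do about as well as SCS patients.** Both systems are marketed, and refusers receive standard care, whose content the protocol does not restrict. In that case type I error is not inflated. Balanced refusals also matter little.
- **Removal from participation is not stated to be exclusion from analysis.** That is correct, and section 4 can be read as keeping refusers in. But no outcome would be collected from them and section 8 is silent, so the conflict remains.
- **A tight margin and small arms do much of the work.** True, but those are the conditions in which this rule will be applied.

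A reader might infer that a couple of refusals in either arm would produce a false noninferiority claim. The documents do not support that, because removing failing SCS refusers works against noninferiority. A reader might also take 13.5% as the expected error. It needs SCS at 81%, whereas 8.3 plans 56% and 1.1 gives 40% to 50%. The rates above 80% in 8.1 concern newer programming and targeted placement, and one source cited there is the trial that supplies the 56%.

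**Conclusion.** The point holds and should be fixed. The text alone establishes three things: refusers are removed and replaced after open randomisation, this is unreconciled with section 4, and section 8 has no all-randomised set.

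The size depends on assumptions that the documents cannot settle. With two DRG refusals, none in SCS, and 26 analysed per arm at an SCS rate of 56%, type I error is about 8.7% if neither refuser would respond, 6.6% at half the completers' rate, and 4.7% at the SCS rate. These are normal approximations. Two failing SCS refusers removed lower power from 78% to 67%.

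It would go too far to say that the rule invalidates the trial or must bias it. At the planned rates the illustrated result survives restoring two failing DRG refusers. The firm criticism is that, with refusers gone and no outcome collected, the plan could not show which scenario had occurred.

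**What to change.** 1. Replace the removal rule in 6.3. Every randomised patient stays in an all-randomised set in the assigned arm, subject to consent for data use. Reconcile sections 4 and 6.3.
2. Before the envelope is opened, confirm that the patient accepts either device.
3. Ask refusers for consent to a 6-month NRS by phone, extending the phone collection in 6.8. Time it from randomisation, because scheduled follow-up runs from implant.
4. Report the all-randomised result with a per-protocol result beside it, and tabulate refusals by arm. Add a sensitivity analysis over refuser outcomes in both arms, including the least favourable case for noninferiority: a missing DRG refuser counted as a non-responder and a missing SCS refuser as a responder. Do not rely on scoring missing as failure in both arms, which is not conservative here (8.8% in the example above).
5. State whether refusers count toward the 62.

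**Cost.** A wording change with IRB approval, one contact per consenting refuser, and some power. Taking 81% as the completers' rate at 26 per arm, one failing DRG refuser gives 0.81×26/27 = 0.78, and power falls from 78% to Φ(0.27/0.1258 − 1.645) = 69%. The power statement in 8.3 should be qualified accordingly. Enrolling more is not the natural answer: holding 70% with one failing DRG refuser needs 27 completers per arm, and 27/0.85 = 31.8, or 64 patients in all, already exceeds the cap of 62. The least favourable case belongs in a sensitivity analysis, because as the primary rule it would cut power to about 66% with one missing refuser per arm and 52% with two.

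Crossover after a failed device trial (6.5) and other attrition need their own analysis rules and are not covered here.

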6.4 Baseline Evaluation

The following evaluations are required at the time of patient screening/baseline.

- Demographic Information: gender, age, weight, height, and smoking status.
- Medical / Surgical History / Previous conservative treatment(s)
- Physical/Neurological Exam
 - Sensory Function/Deficit - Evaluated by the subject's response to light touch and/ or pinprick at infraumbilical dermatome areas.
 - Motor Strength - Evaluated by the subject's ability to contract various muscle groups. Strength will be measured pre-operatively and at each follow-up visit as either:
 - 0 - absent, total paralysis
 - 1 - trace, palpable or visible contraction
 - 2 - poor, active movement through full range of motion (ROM) with gravity eliminated
 - 3 - fair, active movement through full ROM against gravity
 - 4 - good, active movement through full ROM against resistance
 - 5 - normal
- Local tissue temperature asymmetry in the index pain location compared to the contralateral side.

- Pain Assessment: intensity of index pain using a Numerical Rating Scale (NRS)
- Functional Assessment: Oswestry Disability Index (ODI)
- Quality of Life Assessment: EQ-5D
- Health Status Assessment: SF-36
- Pain medication usage (dosage and frequency)
- Patient satisfaction with present treatment strategy

6.5 Procedure

The appropriate procedure will be performed based on the randomization assignment for each patient. Patients randomized to either group will have the device trialed, then implanted according to the standard procedures and practices at our institution.

Those who fail to respond to a trial of the randomized device will have the opportunity to cross over, and retriage the alternative device. Should they have favorable response to the second device, they will proceed to implant of the alternative system.

Any female patient of child bearing age who does not have a documented history of surgical sterilization will have a urine pregnancy test performed within two hours before the device is trialed or implanted.

Pain medications may be administered at the investigator's or prescriber's discretion. A pain medication log will be given to the patient. Continuous pain medication usage will be documented. The treating physician may continue to pharmaceutically manage the patient's pain through the length of the study as clinically indicated. Use of pain medications after either intervention, when compared to pre-intervention dosing, will be considered. The investigator or research coordinator will review the study requirements with the patient in order to maximize compliance with the follow-up schedule and the concomitant medical regimen.

The following parameters for both groups will be noted on the case report forms:

- Index pain location
- Procedure time
- Physical/Neurological Exam
- Complications / Adverse events
- Radiographic Assessment confirming appropriate device placement
- Pain medications

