	
 • Anatomical spinal abnormality including severe central canal stenosis or bony foraminal impingement which could preclude device placement • Foreseen need for MRI to monitor or evaluate another chronic condition • Previous experience with an implanted or trial neuromodulation system (spinal cord stimulation, peripheral nerve stimulation) for the treatment of pain at the index location • Active local or systemic infection • Actively in litigation for pain symptoms • Currently on Workman’s Compensation • Women who are pregnant or intend to become pregnant during the study duration
Study Duration / Follow-up Period	Patients will be followed for an additional 6 months after device implant, with visits at 10 and 30 days, and 3 and 6 months post-procedure. Interim visits for device programming visits will be considered routine.
Baseline Visit	
 • Demographics: gender, age, height, weight • History • Characterization of the inciting event including duration of pain symptoms • Previous treatments including conservative management and physical therapy • Diagnosis and review of the inclusion and exclusion criteria • Neurological assessment • NRS for the index pain location • Pain medication usage (dosage and frequency)
Psychological Assessment	Psychological assessment will consider appropriateness for a neuromodulation system and for participation in a clinical device study.
Pre Trial Visit	
 • Neurological assessment • NRS for the index pain location • ODI • EQ-5D • SF-36 • Satisfaction with baseline management strategy • Pain medication usage (dosage and frequency)

	
 • Presurgical trial evaluation as stratified by the investigator including advanced imaging if necessary • Randomization
Trial Procedure	
 • Neurological assessment • NRS for the index pain location • Pain medication usage (dosage and frequency) • Trial of the study device
Trial Device Removal (7 days postop +/- 3 days)	
 • Wound check, trial device removal • NRS for index site pain • Neurological assessment • Additional intervention(s) • Complications / Adverse events

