1 INTRODUCTION

1.1 Background and Rationale

Complex Regional Pain Syndrome (CRPS) is a constellation of pain symptoms which are associated with impairment in mood, social and physical function (Harden, et al. 2007) (Deer, Levy and Kramer 2017) (Banks and Kerns 1996) (Modovan, et al. 2009). Spinal Cord Stimulation (SCS), a technique of placing electrodes into the epidural space is a validated treatment for Complex Regional Pain Syndrome (Deer, et al. 2014). Treatment of CRPS with SCS, in combination with physical therapy, reduced pain to a greater degree than physical therapy alone (Kemler, et al. 2000). 40%-50% of CRPS patients achieve >50% pain relief with SCS using dorsal column stimulation (Kemler, et al. 2000) (Geurts, et al. 2013). Dorsal Root Ganglion (DRG) SCS has also recently demonstrated clinical efficacy in patients with CRPS and peripheral causalgia (Deer, Levy and Kramer 2017) (Van Buyten, et al. 2015). We hypothesize that DRG stimulation is non-inferior to dorsal column SCS in patients with CRPS who have failed to respond to a course of analgesics and physical therapy. Additionally, we aim to assess functional, quality of life, patient satisfaction and medication requirements in subjects treated with neuromodulation for CRPS and contrast outcomes amongst subjects treated with DRG SCS and dorsal column SCS.

2 Device Indications for Use

DEVICE DESCRIPTIONS

See the manufacturer's Instructions for Use and Surgical Technique Manual for more detailed information.

The Nuvectra Algovita Dorsal Column Spinal Cord Stimulator is indicated as an aid in the management of chronic intractable pain of the trunk and/or limbs, including unilateral or bilateral pain associated with failed back surgery syndrome, intractable low back pain and leg pain.

The Axiom Neurostimulator System is indicated for spinal column stimulation via epidural and intra-spinal lead access to the dorsal root ganglion as an aid in the management of moderate to severe chronic intractable pain of the lower limbs in adult patients with Complex Regional Pain Syndrome Types I and II

Systems that will be utilized in this study are indicated for use in this condition and have already been cleared for marketing by the FDA.

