3 STUDY PURPOSE AND OBJECTIVE

The purpose of this study is to compare outcomes between dorsal column spinal cord stimulation and dorsal root ganglion spinal cord stimulation in patients with Complex Regional Pain Syndrome at an infraumbilical location who have failed a course of conservative management including analgesic pharmacotherapy and physical therapy.

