4.1 Primary Endpoint

- The primary endpoint in this study is 50% change in index pain using a Numerical Rating Scale (NRS) at 6 months

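### Patients who fail the trial of their randomised device may be implanted with the comparator, but the primary analysis does not say on which device success must occur, in which arm crossovers count, or how double trial failures are scored.

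*Combined protocol and SAP*

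**What the plan says.** Section 6.3 randomises patients 1:1 to a device, unmasked, before any trial of it. Section 6.5 then provides: "Those who fail to respond to a trial of the randomized device will have the opportunity to cross over". It continues: "Should they have favorable response to the second device, they will proceed to implant of the alternative system". Implanting the comparator is therefore a planned pathway, not a deviation.

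The hypothesis in section 1.1 is about the devices: "We hypothesize that DRG stimulation is non-inferior to dorsal column SCS in patients with CRPS". Section 3 gives the same purpose: "The purpose of this study is to compare outcomes between dorsal column spinal cord stimulation and dorsal root ganglion spinal cord stimulation".

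The endpoint in section 4.1 is not tied to a device: "The primary endpoint in this study is 50% change in index pain using a Numerical Rating Scale (NRS) at 6 months". Section 8.3 defines success as a reduction of at least 50% in index-area NRS, and section 8.4 compares success rates between the two treatment arms. Neither says whether a crossover counts in the assigned arm or in the arm of the implanted device.

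On who is counted, section 4 says: "The following endpoints will be evaluated in all patients enrolled in the study". Section 5.2 sets a "target maximum of 62 patients (31 randomized to each group"), and section 8.3 uses the same 31 per arm. The follow-up clock, however, starts at implant. The synopsis says: "Patients will be followed for an additional 6 months after device implant", and section 5.3 times its visits the same way.

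Section 6.3 does have a rule for patients who refuse their assignment: they are removed and replaced. There is no corresponding rule for patients who fail one trial or both.

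**The concern.** Three kinds of patient need a rule: those who respond to the randomised device, those who fail its trial and are implanted with the other system, and those who fail both trials. Only the first has a clear place in the primary analysis.

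The gap can be filled in three ways:

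- **By randomised arm, relief on any device.** A patient who fails dorsal column SCS and is relieved by DRG is an SCS success, and the reverse. The contrast is between two strategies: start with this device, and switch if its trial fails.
- **By implanted device.** The contrast is between devices, but the groups are no longer those formed by randomisation. Patients who failed one trial move into the other group.
- **Implanted patients only.** Patients who fail both trials drop out of the denominator because of how they responded to treatment.

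None of these gives a randomised comparison of the two devices. A noninferiority result would be read as a statement about the devices, although part of an arm's success may come from the other one. In an unmasked trial, a choice left until outcomes are visible may also be influenced by them.

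**Working it through.** **Inputs from the documents.** Section 8.3: success 81% (DRG) and 56% (SCS), 31 per arm, 15% attrition, margin 5 points. Section 8.4: one-sided 0.05. Evaluable per arm: 31 × 0.85 = 26.35, taken as 26.

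**Inputs assumed.** The documents give no trial-failure or rescue rates. Let *fail* be the proportion of an arm that fails the trial of its randomised device. Let *rescue* be the proportion of those who are implanted with the other device and succeed at 6 months. I also assume that 81% and 56% are rates per randomised patient on the randomised device, which section 8.3 does not confirm. The failure rates used fit within the own-device non-success of 19% (DRG) and 44% (SCS).

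**Formula.** Power = Φ((p_DRG − p_SCS + 0.05)/SE − 1.645), with SE = √[p_DRG(1 − p_DRG)/26 + p_SCS(1 − p_SCS)/26].

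**Step 1: the plan's figure.** SE = √(0.81×0.19/26 + 0.56×0.44/26) = 0.1241. Then 0.30/0.1241 − 1.645 = 0.773, so power is 78.0%. Exact enumeration of the same test gives 77.3%. Both agree with the more than 70% stated in 8.3.

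**Step 2: crossover success credited to the randomised arm.** Arm rate = own-device rate + fail × rescue, with double failures kept as non-responders.

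| Trial failure DRG/SCS | Rescue | DRG v SCS arm | Power |
|---|---|---|---|
| 10%/10% | 20% | 83% v 58% | 79.4% |
| | 30% | 84% v 59% | 80.2% |
| | 50% | 86% v 61% | 81.9% |
| | other device's full rate | 86.6% v 64.1% | 77.0% |
| 10%/20% | 20% | 83% v 60% | 74.8% |
| | 30% | 84% v 62% | 73.2% |
| | 50% | 86% v 66% | 70.1% |
| | other device's full rate | 86.6% v 72.2% | 54.5% |
| 10%/30% | 20% | 83% v 62% | 69.7% |
| | 30% | 84% v 65% | 65.2% |
| | 50% | 86% v 71% | 55.6% |
| | other device's full rate | 86.6% v 80.3% | 29.3% |

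In the full-rate rows, DRG-arm failures succeed on SCS at 56% and SCS-arm failures succeed on DRG at 81%. For example, 0.81 + 0.10×0.56 = 0.866 and 0.56 + 0.20×0.81 = 0.722. These rows are extremes, since they assume that failing one trial says nothing about the other device.

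**Step 3: DRG truly worse by exactly the margin (61% v 66%).** On an own-device basis the chance of declaring noninferiority is 5.0%. With DRG/SCS trial failure of 20%/10%, 30% rescue gives 67% v 69% and 7.9%, and 50% rescue gives 71% v 71% and 10.6%. With 20%/20% failure and 50% rescue it is 71% v 76% and remains 5.0%.

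**Step 4: double trial failures.** No arithmetic is needed to see the gap. Section 4 evaluates all enrolled patients, while the synopsis and 5.3 time the 6-month visit from implant. A patient who is never implanted belongs to the first group and has no such visit. I put no figure on leaving these patients out, because that needs a further assumed rate, namely how many crossovers pass the second trial.

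**The case against.** **The plan does not commit to a strategy comparison.** A reader might infer that the analysis as written already answers the wrong question. The documents do not support that. Sections 4, 5.2 and 8.3 point towards analysis by randomised arm, but no analysis population is stated and an as-implanted reading is open. What stands is that the rule is missing and that each way of filling the gap departs from the hypothesis.

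**A strategy comparison is legitimate.** The title calls this a comparative effectiveness study, and crediting outcomes to the assigned arm is conventional. This is right, but the hypothesis and purpose would have to say so, and double failures would still need a score.

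**The sizes rest on assumed rates.** This is also right. Six of the nine equal-rescue cases stay above 70%, and a seventh is 69.7%. The power gain at 10%/10% comes from assuming equal rescue in both arms; at the other device's full rate, power is 77.0%, slightly below the 78.0% baseline.

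**A tempting stronger claim is that crossover biases the trial towards DRG.** Under the plan's own rates DRG is better, and in most of the cases above crediting crossovers costs power. The rise to 8–11% requires DRG to be worse, to fail more trials, and to be judged on an own-device estimand. For a strategy estimand the 71% v 71% case is true equality, so declaring noninferiority there is not an error.

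**Attrition might cover never-implanted patients.** Section 8.3 does not say. Crossovers, in any case, stay in follow-up and contribute outcomes.

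**Figure 1 is not available here.** It may show the crossover path, but section 8.4 is where a scoring rule belongs, and it contains none.

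**Conclusion.** The point holds and should be settled before outcomes are examined. The plan allows implant of the comparator after trial failure, and it does not say which device must produce success, which arm a crossover belongs to, or how a patient who fails both trials is scored. This goes beyond missing detail, because the choice changes both the question answered and the denominator.

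The size is illustrative only. At 26 per arm, one-sided 0.05 and 81% v 56%, own-device power is 78%. Credited by randomised arm with equal rescue of 20–50%, it is about 79–82%, 70–75% and 56–70% for DRG/SCS trial failure of 10%/10%, 10%/20% and 10%/30%. With rescue at the other device's full rate it is 77%, 54.5% and 29%. The effect is small when trial failure is equal in the two arms and large when SCS fails many more trials and rescue is high. The documents do not show which case applies, and they do not show that the trial would reach a false conclusion.

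**What to change.** In section 8.4, state that all randomised patients are analysed by assigned arm, and choose one estimand.

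- **To match the hypothesis in 1.1:** define primary success as a reduction of at least 50% in index NRS at 6 months on the randomised device. Count every patient who fails that device's trial, crossovers and double failures alike, as a non-responder in the assigned arm and in its denominator. Report outcomes after crossover separately, with the any-device, as-randomised analysis as a sensitivity analysis.
- **If the strategy comparison is intended:** say so in the objective and in 8.4, score double trial failures as non-responders in the assigned arm, and make the own-device analysis the sensitivity analysis.

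In section 8.3, state whether 81% and 56% are on the chosen basis and whether the 15% attrition includes patients who are never implanted. If the rates are not on that basis, restate the power.

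The cost is wording in 8.3 and 8.4, plus the objective under the second option. No visits are added, and patients are added only if the restated power proves too low. The downside is that success rates per randomised patient will be lower than rates per implant. The crossover option itself need not change.
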